### PAIN

		0	1	2	3	4
P1	How often do you experience knee pain?	 Never	 Monthly	 Weekly	 Daily	 Always

What amount of knee pain have you experienced the last week during the following activities?

		0	1	2	3	4
P2	Twisting/pivoting on your knee	 None	 Mild	 Moderate	 Severe	 Extreme
P3	Straightening knee fully	 None	 Mild	 Moderate	 Severe	 Extreme
P4	Bending knee fully	 None	 Mild	 Moderate	 Severe	 Extreme
P5	Walking on flat surface	 None	 Mild	 Moderate	 Severe	 Extreme
P6	Going up or down stairs	 None	 Mild	 Moderate	 Severe	 Extreme
P7	At night while in bed	 None	 Mild	 Moderate	 Severe	 Extreme
P8	Sitting or lying	 None	 Mild	 Moderate	 Severe	 Extreme
P9	Standing upright	 None	 Mild	 Moderate	 Severe	 Extreme

## ADL

**Function, daily living:** The following questions concern your physical function. By this we mean your ability to move around and to look after yourself. For each of the following activities please indicate the degree of difficulty you have experienced in the **last week** due to your knee.

		0	1	2	3	4
A1	Descending stairs	 None	 Mild	 Moderate	 Severe	 Extreme
A2	Ascending stairs	 None	 Mild	 Moderate	 Severe	 Extreme

For each of the following activities please indicate the degree of difficulty you have experienced in the last week due to your knee.

		0	1	2	3	4
A3	Rising from sitting	 None	 Mild	 Moderate	 Severe	 Extreme
A4	Standing	 None	 Mild	 Moderate	 Severe	 Extreme
A5	Bending to floor/pick up an object	 None	 Mild	 Moderate	 Severe	 Extreme
A6	Walking on flat surface	 None	 Mild	 Moderate	 Severe	 Extreme
A7	Getting in/out of car	 None	 Mild	 Moderate	 Severe	 Extreme
A8	Going shopping	 None	 Mild	 Moderate	 Severe	 Extreme
A9	Putting on socks/stockings	 None	 Mild	 Moderate	 Severe	 Extreme
A10	Rising from bed	 None	 Mild	 Moderate	 Severe	 Extreme
A11	Taking off socks/stockings	 None	 Mild	 Moderate	 Severe	 Extreme
A12	Lying in bed (turning over, maintaining knee position)	 None	 Mild	 Moderate	 Severe	 Extreme
A13	Getting in/out of bath	 None	 Mild	 Moderate	 Severe	 Extreme
A14	Sitting	 None	 Mild	 Moderate	 Severe	 Extreme
A15	Getting on/off toilet	 None	 Mild	 Moderate	 Severe	 Extreme

For each of the following activities please indicate the degree of difficulty you have experienced in the last week due to your knee.

		0	1	2	3	4
A16	Heavy domestic duties (moving heavy boxes, scrubbing floors, etc.)	 None	 Mild	 Moderate	 Severe	 Extreme
A17	Light domestic duties (cooking, dusting, etc.)	 None	 Mild	 Moderate	 Severe	 Extreme

## SPORT/REC

### Function, sports and recreational activities

The following questions concern your physical function when being active on a higher level. The questions should be answered thinking of what degree of difficulty you have experienced during the **last week** due to your knee.

		0	1	2	3	4
SP1	Squatting	 None	 Mild	 Moderate	 Severe	 Extreme
SP2	Running	 None	 Mild	 Moderate	 Severe	 Extreme
SP3	Jumping	 None	 Mild	 Moderate	 Severe	 Extreme
SP4	Twisting/pivoting on your injured knee	 None	 Mild	 Moderate	 Severe	 Extreme
SP5	Kneeling	 None	 Mild	 Moderate	 Severe	 Extreme

### QUAITY OF LIFE

		0	1	2	3	4
Q1	How often are you aware of your knee problem?	 Never	 Monthly	 Weekly	 Daily	 Constantly
Q2	Have you modified your life style to avoid potentially damaging activities to your knee?	 Not at all	 Mildly	 Moderately	 Severely	 Totally
Q3	How much are you troubled with lack of confidence in your knee?	 Not at all	 Mildly	 Moderately	 Severely	 Extremely
Q4	In general, how much difficulty do you have with your knee?	 None	 Mild	 Moderate	 Severe	 Extreme

Thank you very much for completing all the questions in this questionnaire.

---

### **Score (by Study Coordinator):**

KOOS Symptoms       $100 - (\text{Mean score of S1 to S7 } \underline{\hspace{2cm}} \times 25) = \underline{\hspace{2cm}}$

KOOS Pain       $100 - (\text{Mean score of P1 to P9 } \underline{\hspace{2cm}} \times 25) = \underline{\hspace{2cm}}$

KOOS ADL       $100 - (\text{Mean score of A1 to A17 } \underline{\hspace{2cm}} \times 25) = \underline{\hspace{2cm}}$

KOOS Sport/Rec       $100 - (\text{Mean score of SP1 to SP5 } \underline{\hspace{2cm}} \times 25) = \underline{\hspace{2cm}}$

KOOS QOL       $100 - (\text{Mean score of Q1 to Q4 } \underline{\hspace{2cm}} \times 25) = \underline{\hspace{2cm}}$

Signature: \_\_\_\_\_ Date: \_\_\_\_\_

## Appendix 7. International Knee Documentation Committee (IKDC) Subjective Knee Evaluation

Site No: \_\_

Subject No: \_\_ \_\_

Subject Initials: \_\_ \_\_ \_\_

Visit (circle one): Baseline M1 M3 M6 M9 M12 ET ( / / ) Final FU ( / / )

### SYMPTOMS:

Grade symptoms at the highest activity level at which you think you could function without significant symptoms, even if you are not actually performing activities at this level.

1. What is the highest level of activity that you can perform without significant knee pain?

4  Very strenuous activities like jumping or pivoting as in basketball or soccer  
3  Strenuous activities like heavy physical work, skiing or tennis  
2  Moderate activities like moderate physical work, running or jogging  
1  Light activities like walking, housework or yard work  
0  Unable to perform any of the above activities due to knee pain

2. During the past 4 weeks, or since your injury, how often have you had pain?

0	1	2	3	4	5	6	7	8	9	10
Never 	 Constant									

3. If you have pain, how severe is it?

0	1	2	3	4	5	6	7	8	9	10
No pain 	 Worst pain									

4. During the past 4 weeks, or since your injury, how stiff or swollen was your knee?

4  Not at all  
3  Mildly  
2  Moderately  
1  Very  
0  Extremely

5. What is the highest level of activity you can perform without significant swelling in your knee?

4  Very strenuous activities like jumping or pivoting as in basketball or soccer  
3  Strenuous activities like heavy physical work, skiing or tennis  
2  Moderate activities like moderate physical work, running or jogging  
1  Light activities like walking, housework, or yard work  
0  Unable to perform any of the above activities due to knee swelling

6. During the past 4 weeks, or since your injury, did your knee lock or catch?

0  Yes 1  No

7. What is the highest level of activity you can perform without significant giving way in your knee?

4  Very strenuous activities like jumping or pivoting as in basketball or soccer  
3  Strenuous activities like heavy physical work, skiing or tennis  
2  Moderate activities like moderate physical work, running or jogging  
1  Light activities like walking, housework or yard work  
0  Unable to perform any of the above activities due to giving way of the knee

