**Score (by Study Coordinator)**

IKDC Score = (Sum of Items: \_\_\_\_\_) / (Maximum Possible Score: 87) x 100 = \_\_\_\_\_

\* The response to Item 10a is not included in the overall score.

Signature: \_\_\_\_\_ Date: \_\_\_\_\_

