6.2.6 IKDC

IKDC will be collected at Visits 3, 4, 5, 6, 7 and 8 (Baseline, M1, M3, M6, M9 and M12) or Early Termination (only if the subject is early terminated after Visit 3) or Final Follow-up Visit. Summary statistics of IKDC will be presented by visit and treatment group. The change from baseline will also be calculated and represented in summary table.

① Change of IKDC from baseline at Month 6 (JointStem group vs. positive control group)

This secondary efficacy endpoint will be analyzed with an ANCOVA with factors of treatment and the baseline of IKDC as a covariate. Model-based LS Means of the differences between study and control groups, along with 95% CI and p-value will be provided.

② Change of IKDC from baseline at Months 6, 9 and 12 (JointStem group)

Change of IKDC from baseline at Months 6, 9 and 12 will be analyzed using paired t-test (two-sided test, $\alpha=0.05$) with the null hypothesis equal to zero. The number of patients, mean, standard deviation, minimum (min) and maximum (max) values for the baseline, months 6, months 9, months 12 and change from baseline will be calculated and reported in summary table. The 95% CI and p-value will also be provided. Shapiro-Wilks test will be used to test the normality of change of IKDC from baseline at Months 6, 9 and 12. If change of IKDC from baseline at Months 6, 9 and 12 doesn't satisfy normal distribution, Wilcoxon signed rank test will be performed.

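### The IKDC scoring sheet sums the two 0–10 pain items without reversing them, so pain relief lowers the score and a pain-free normal knee scores 77 rather than 100

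*Protocol*

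**What the plan says.** Protocol Appendix 7 contains the IKDC form and its scoring line. The two pain items under Symptoms are item 2, "During the past 4 weeks, or since your injury, how often have you had pain", and item 3, "If you have pain, how severe is it". Both are marked from 0 to 10. On item 2, 0 stands at Never and 10 at Constant; on item 3, 0 stands at No pain and 10 at Worst pain.

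The other scored items run the opposite way. Item 1, "What is the highest level of activity that you can perform without significant knee pain", gives 4 to very strenuous activity. Item 4, "During the past 4 weeks, or since your injury, how stiff or swollen was your knee", gives 4 to the knee with no stiffness or swelling. Item 6 gives 1 for no locking, items 9a to 9i give 4 for no difficulty, and current function (10b) gives 10 for normal.

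The coordinator's formula is the sum of items over "Maximum Possible Score: 87) x 100". Its one special rule is that "The response to Item 10a is not included in the overall score".

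The SAP does not redefine the score. Section 6.2.6 compares the arms at Month 6 with an "ANCOVA with factors of treatment and the baseline of IKDC as a covariate", and tests change within JointStem at Months 6, 9 and 12 with a paired t-test or Wilcoxon signed rank test.

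**The concern.** A summed score has a meaning only if all its items point the same way. Here 67 of the 87 points rise as the knee gets better and 20 rise as it gets worse. A patient whose pain is relieved loses IKDC points on items 2 and 3.

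Pain is what the trial aims to relieve: subjects need a VAS of at least 40 mm to enter, and change in VAS is a co-primary endpoint. The inverted items are therefore ones expected to move. The error is not random noise, because it penalises whichever arm relieves more pain. It also enters the baseline score, so the ANCOVA covariate is mis-scored too. With a planned 20 and 10 subjects, a between-arm difference that has been shrunk in this way could easily be missed, and in some patterns of response it would change sign.

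**Working it through.** **Inputs**, all from Protocol Appendix 7:

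| Item | Range | Higher number means |
|---|---|---|
| 1, activity without pain | 0–4 | better |
| 2, pain frequency | 0–10 | **worse** |
| 3, pain severity | 0–10 | **worse** |
| 4, stiffness or swelling | 0–4 | better |
| 5, activity without swelling | 0–4 | better |
| 6, locking or catching | 0–1 | better |
| 7, activity without giving way | 0–4 | better |
| 8, regular activity level | 0–4 | better |
| 9a–9i, nine abilities | 9 × (0–4) = 0–36 | better |
| 10b, current function | 0–10 | better |

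**Reproducing the printed maximum.** 4 + 10 + 10 + 4 + 4 + 1 + 4 + 4 + 36 + 10 = 87, which matches. Without items 2 and 3 the total would be 67; with 10a it would be 97. So both pain items are in the sum, at up to 10 points each.

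**Ends of the scale as printed** (sum / 87 × 100):

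- Pain-free knee, best on every other item: 87 - 20 = 67, and 67/87 × 100 = 77.0.
- Constant, worst pain and worst on every other item: 20/87 × 100 = 23.0.
- The distance from worst to best knee is 77.0 - 23.0 = 54.0 points instead of 100.
- A score of 100 needs constant, worst pain together with perfect answers elsewhere.

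**Effect on change scores:**

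- One point of relief on either pain item: -1/87 × 100 = -1.15, where +1.15 is intended.
- Both pain items improve by 5, nothing else changes (assumed): -10/87 × 100 = -11.5 instead of +11.5.
- Both pain items go from 7 to 3, nothing else changes (assumed): -8/87 × 100 = -9.2 instead of +9.2, an error of 18.4 points.
- Every item improves by 20% of its range (assumed): (67 - 20) × 0.20 / 87 × 100 = +10.8 instead of +20, so 46% of the change is lost.

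**When the sign reverses.** The recorded change is negative for a patient who has improved when the points gained on items 2 and 3 exceed those gained on all other items. Expressed as fractions of range, the pain items must improve more than 67/20 = 3.35 times as much as the rest.

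**With the reversal** (items 2 and 3 as 10 minus the response): the best knee scores 87/87 × 100 = 100 and the worst 0/87 × 100 = 0.

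**Search for a reversal elsewhere.** Protocol 6.1.5 and SAP 6.2.6 use the IKDC score without defining it. The neighbouring sheets do print their conversions: Appendix 6 computes each KOOS subscale as 100 minus 25 times the item mean, and Appendix 8 gives a recoding table for the RAND-36 items. Appendix 7 has no equivalent step.

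**The case against.** The documents never say in words that a higher IKDC score is better. That is an inference, but a strong one: it follows from 67 of the 87 points, including 10b, where 10 is normal function.

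A reversal might sit in eCRF programming or in scoring instructions outside these documents. SAP 2.1 speaks of eCRF data and derived variables, and nothing says whether the analysed IKDC value is the coordinator's total or is re-derived from the items. This stands as a limit: the documents show a missing rule, not that mis-scored data were analysed. It does not rescue the plan, because the printed formula is the only definition given and a coordinator who follows it will get the wrong total.

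The item grids were read from extracted text. Both show 0 first, beside the no-pain label, and 10 last, beside the worst-pain label, and nothing suggests another alignment.

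On size, the -11.5 example is an extreme case. Item 1 also concerns pain, is coded the right way, and would probably move as well. A sign reversal needs the pain items to improve far more than the rest, and the 20% example keeps its sign. The 46% loss is in score units under equal proportional improvement. The effect on the test statistics depends on item variances and correlations that the documents do not give.

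Finally, IKDC is one of six scales compared between the arms as secondary endpoints in a proof-of-concept study with no formal sample size calculation. That limits the reach of the error but does not make the score valid.

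**Conclusion.** The concern holds. Scored as Appendix 7 instructs, 20 of 87 IKDC points (23%) are inverted, the scale from worst to best knee runs from 23.0 to 77.0, and relief of pain counts against the patient. The loss is 46% of the change under a uniform proportional improvement. It is larger, up to a reversed sign, when improvement is concentrated in the two pain items.

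This rests on the printed number-to-label alignment, on higher IKDC meaning a better knee, and on the form being scored as written. The change-score examples use assumed responses.

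The analyses affected are IKDC between the arms at Month 6, within JointStem at Months 6, 9 and 12, and in the exploratory Month 24 follow-up. The WOMAC, VAS and MRI co-primary endpoints are untouched. It must still be fixed, because a prespecified secondary endpoint is wrong as defined.

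**What to change.** In Protocol Appendix 7 and SAP 6.2.6, state that items 2 and 3 enter the sum as 10 minus the marked value, that the divisor stays at 87, and that the score runs from 0 (worst) to 100 (best). State in SAP 6.2.6 that the analysed IKDC score is derived from item-level responses, not taken from the coordinator's total. Re-score every form already totalled with the printed formula, baseline forms included. If a reversal is already programmed elsewhere, document it in both places and confirm that it is applied only once.

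The cost is a sentence or two in each document and a re-derivation from responses already on the forms. No new data or patients are needed.

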**SPORTS ACTIVITIES:**

8. What is the highest level of activity you can participate in on a regular basis?

4  Very strenuous activities like jumping or pivoting as in basketball or soccer  
3  Strenuous activities like heavy physical work, skiing or tennis  
2  Moderate activities like moderate physical work, running or jogging  
1  Light activities like walking, housework or yard work  
0  Unable to perform any of the above activities due to knee

[figure not shown]
9. How does your knee affect your ability to:

		Not difficult at all	Minimally difficult	Moderately Difficult	Extremely difficult	Unable to do
a.	Go up stairs	4 	3 	2 	1 	0 
b.	Go down stairs	4 	3 	2 	1 	0 
c.	Kneel on the front of your knee	4 	3 	2 	1 	0 
d.	Squat	4 	3 	2 	1 	0 
e.	Sit with your knee bent	4 	3 	2 	1 	0 
f.	Rise from a chair	4 	3 	2 	1 	0 
g.	Run straight ahead	4 	3 	2 	1 	0 
h.	Jump and land on your involved leg	4 	3 	2 	1 	0 
i.	Stop and start quickly	4 	3 	2 	1 	0 

[figure not shown]
**FUNCTION:**

10. How would you rate the function of your knee on a scale of 0 to 10 with 10 being normal, excellent function and 0 being the inability to perform any of your usual daily activities which may include sports?

FUNCTION PRIOR TO YOUR KNEE INJURY:

CURRENT FUNCTION OF YOUR KNEE:

Thank you very much for completing all the questions in this questionnaire.

**Score (by Study Coordinator)**

IKDC Score = (Sum of Items: \_\_\_\_\_) / (Maximum Possible Score: 87) x 100 = \_\_\_\_\_

\* The response to Item 10a is not included in the overall score.

Signature: \_\_\_\_\_ Date: \_\_\_\_\_

## Appendix 8. RAND 36 Questionnaires

Site No: \_\_

Subject No: \_\_ \_\_

Subject Initials: \_\_ \_\_ \_\_

Visit (circle one): Baseline M3 M6 M9 M12 ET ( / / ) Final FU ( / / )

1. In general, would you say your health is: (circle one)  
Excellent (1) Very good (2) Good (3) Fair (4) Poor (5)
2. **Compared to one year ago**, how would you rate your health in general now? (circle one)  
Much better now than one year ago (1) Somewhat better now than one year ago (2)  
About the same as one year ago (3) Somewhat worse than one year ago (4)  
Much worse than one year ago (5)

The following items are about activities you might do during a typical day. Does **your health now limit you** in these activities? If so, how much? (circle one number on each line)

ACTIVITIES	Yes, Limited A Lot	Yes, Limited A Little	No, Not Limited At All
3. Vigorous activities , such as running, lifting heavy objects, participating in strenuous sports	1	2	3
4. Moderate activities , such as moving a table, pushing a vacuum cleaner, bowling, or playing golf	1	2	3
5. Lifting or carrying groceries	1	2	3
6. Climbing several flights of stairs	1	2	3
7. Climbing one flight of stairs	1	2	3
8. Bending, kneeling or stooping	1	2	3
9. Walking more than a mile	1	2	3
10. Walking several blocks	1	2	3
11. Walking one block	1	2	3
12. Bathing or dressing yourself	1	2	3

During the **past 4 weeks**, have you had any of the following problems with your work or other regular daily activities **as a result of your physical health**? (circle one number on each line)

	Yes	No
13. Cut down on the amount of time you spent on work or other activities	1	2
14. Accomplished less than you would like	1	2
15. Were limited in the kind of work or other activities	1	2
16. Had difficulty performing the work or other activities (for example, it took extra effort)	1	2

During the **past 4 weeks**, have you had any of the following problems with your work or other regular daily activities **as a result of any emotional problems** (such as feeling depressed or anxious)? (circle one number on each line)

	Yes	No
17. Cut down the amount of time you spent on work or other activities	1	2

18. Accomplished less than you would like	1	2
19. Didn't do work or other activities as carefully as usual	1	2

20. During **the past 4 weeks**, to what extent has your physical health or emotional problems interfered with your normal social activities with family, friends, neighbors or groups? (circle one)

Not at all (1) Slightly (2) Moderately (3) Quite a bit (4) Extremely (5)

21. How much **bodily** pain have you had during the **past 4 weeks**? (circle one)

None (1) Very mild (2) Mild (3) Moderate (4) Severe (5) Very severe (6)

22. During the **past 4 weeks**, how much did **pain** interfere with your normal work (including both work outside the home and housework)?

Not at all (1) A little bit (2) Moderately (3) Quite a bit (4) Extremely (5)

These questions are about how you feel and how things have been with you **during the past 4 weeks**. For each question, please give the one answer that comes closest to the way you have been feeling. How much of the time during the **past 4 weeks**... (circle one number on each line)

	All of the Time	Most of the Time	A Good Bit of the Time	Some of the Time	A Little of the Time	None of the Time
23. Did you feel full of pep?	1	2	3	4	5	6
24. Have you been a very nervous person?	1	2	3	4	5	6
25. Have you felt so down in the dumps that nothing could cheer you up?	1	2	3	4	5	6
26. Have you felt calm and peaceful?	1	2	3	4	5	6
27. Did you have a lot of energy?	1	2	3	4	5	6
28. Have you felt downhearted and blue?	1	2	3	4	5	6
29. Did you feel worn out?	1	2	3	4	5	6
30. Have you been a happy person?	1	2	3	4	5	6
31. Did you feel tired?	1	2	3	4	5	6

32. During the **past 4 weeks**, how much of the time has your **physical health or emotional problems** interfered with your social activities (like visiting with friends, relatives, etc.)? (circle one)

All of the time (1) Most of the time (2) Some of the time (3) A little of the time (4) None of the time (5)

How TRUE or FALSE is each of the following statements for you? (circle one number on each line)

	Definitely True	Mostly True	Don't Know	Mostly False	Definitely False
33. I seem to get sick a little easier than other people	1	2	3	4	5
34. I am as healthy as anybody I know	1	2	3	4	5
35. I expect my health to get worse	1	2	3	4	5
36. My health is excellent	1	2	3	4	5

Thank you very much for completing all the questions in this questionnaire.

**Scores (by Study Coordinator):**

Item Numbers	Response	Score	Item Numbers	Response	Score
1, 2, 20, 22, 34, 36	1	100	32, 33, 35	1	0
	2	75		2	25
	3	50		3	50
	4	25		4	75
	5	0		5	100
3, 4, 5, 6, 7, 8, 9, 10, 11, 12	1	0	13, 14, 15, 16, 17, 18, 19	1	0
	2	50		2	100
	3	100			
21, 23, 26, 27, 30	1	100	24, 25, 28, 29, 31	1	0
	2	80		2	20
	3	60		3	40
	4	40		4	60
	5	20		5	80
	6	0		6	100

	Items	Score (Mean)
Physical Functioning	3, 4, 5, 6, 7, 8, 9, 10, 11, 12	Total: _____ / 10 = _____
Role Limitation (Physical)	13, 14, 15, 16	Total: _____ / 4 = _____
Role Limitation (Emotional)	17, 18, 19	Total: _____ / 3 = _____
Energy/fatigue	23, 27, 29, 31	Total: _____ / 4 = _____
Emotional well-being	24, 25, 26, 28, 30	Total: _____ / 5 = _____
Social Functioning	20, 32	Total: _____ / 2 = _____
Pain	21, 22	Total: _____ / 2 = _____
General Health	1, 2, 33, 34, 35, 36	Total: _____ / 6 = _____

Signature: \_\_\_\_\_ Date: \_\_\_\_\_

## Appendix 9. MRI Improvement Evaluation

### MRI Improvement Evaluation Form

Protocol Number: JS-OAP2-US01

Site No.	Subject No.	Subject Initials

■ The time of Evaluation (from Baseline):

 From baseline at Month 6
 From baseline at Month 12

■ Principal Investigator's MRI Final Evaluation:

► Please select one of 3 followings for MRI result at above checked time.

	Ⓐ Improvement
<hr/>	
	Ⓑ No change
	Ⓒ Progress

■ Evaluated by:

Principal Investigator

---

Name / Signature

---

Date (DD-MMM-YYYY)

| 7.3 | VITAL SIGNS, PHYSICAL EXAMINATIONS FINDINGS, ECG | 20 |
| 7.3.1 | Vital Signs | 20 |
| 7.3.2 | Physical Examinations | 20 |
| 7.3.3 | ECG | 21 |
| 8. | INTERIM ANALYSES AND DATA AND SAFETY MONITORING BOARD (DSMB) | 21 |
| 8.1 | INTERIM ANALYSES | 21 |
| 8.2 | DSMB | 21 |
| 9. | SUMMARY OF MAJOR CHANGES IN THE PLANNED ANALYSES | 21 |

ABBREVIATIONS

| Abbreviation | Term |
|---------------------|---|
| AdMSC | Adipose Tissue Derived Mesenchymal Stem Cell |
| AEs | Adverse Events |
| ALT | Alanine Aminotransferase |
| ANCOVA | Analysis of Covariance |
| AST | Aspartate Aminotransferase |
| ATC | Anatomical Therapeutic Chemical |
| BMI | Body Mass Index |
| BP | Blood Pressure |
| BUN | Blood Urea Nitrogen |
| DSMB | Data and Safety Monitoring Board |
| ECG | Electrocardiogram |
| eCRF | Electronic Case Report Form |
| IKDC | International Knee Documentation Committee |
| ITT | Intention-to-Treat |
| KOOS | Knee Injury & Osteoarthritis Outcome Score |
| LS Means | Least square adjusted means |
| LOCF | Last-Observation-Carry-Forward |
| MedDRA | Medical Dictionary For Regulatory Activities |
| MRI | Magnetic Resonance Imaging |
| PP | Per Protocol |
| PT | Preferred Term |
| PT-INR | Prothrombin Time - International Normalized Ratio |
| SAE | Serious Adverse Event |
| SAP | Statistical Analysis Plan |
| SD | Standard Deviation |
| SI | Système International |
| SOC | System Organ Class |
| TEAE | Treatment-Emergent Adverse Event |
| VAS | Visual Analog Scale |
| WHO | World Health Organization |
| WOMAC | Western Ontario and McMaster Universities Arthritis Index |

